5.5 Withdrawal of subjects from study

Subjects are allowed to decline further participation in the study at any time. This will not affect their future care.

5.6 Study timelines

Recruitment and baseline visits (visit 1) will take place from months 1-12, with annual visits from months 13-24 (visit 2) and 25-36 (visit 3)

5.7 Sub-Study

- A sub-study will be conducted at the St Mary's Hospital site for participants equal to and over the age of 50 both HIV +ve and HIV -ve.

The protocol for this sub-study is entitled "The POPPY St. Mary's MRI Sub-study".

- Participants may be invited to participate in linked sub-studies that have been approved by the steering committee. Separate protocols, information sheets and consents would be produced for each sub-study.

5.8 End of trial definition

The end of the trial will be the last data capture for the last patient recruited to the POPPY study.

6.0 Study Specific Procedures

6.1 DEXA scanning

All study subjects will undergo a regional (hip and spine) and whole body DXA scan where available (only if urinary β hcg is negative in female subjects under the age of 50). Total and regional bone mineral density Z and T scores will be estimated and total and regional fat and lean mass calculated. All scans will be performed by medical staff and reported by a consultant radiologist and should be performed within 30 days of the clinic visit.

The reports of the scans will be sent to the patients GPs where permission for contact is in place. In the cases where no permission is granted for GP contact, the results will be sent to the health care professional in charge of that patient within the clinic. In all cases any abnormalities detected will therefore be actioned.

6.2 Blood sampling

Pharmacokinetic sampling

Prior to blood taking for pharmacokinetic sampling, time of food intake nearest last dose prior to sampling and food content will be recorded (fasting, light snack, heavy meal). Time of last dose and time of sampling will be recorded.

Efforts will allow for blood sample collection at least 5 hours after the drug dose is administered in order to ensure the sample is post-absorption and to enable the modeling of sparse data.

Blood sample (4-5 mL in EDTA or lithium heparin) collections for the determination of the plasma concentrations of tenofovir and the third agent (i.e. a non-nucleoside reverse transcriptase, protease, entry or integrase inhibitor) in the patient's regimen will be drawn at steady-state. Samples will be processed to isolate plasma and stored at -20°C until shipment to the central laboratory at the University of Liverpool for analysis.

Blood for storage

Blood (serum and plasma,) and urine samples will be collected at visits 1 and 3 stored for subsequent projects of the potential pathogenic mechanisms underlying age-related diseases. This will include assessment of vitamin-D and PTH and probably DNA analysis. Approximately 20mls of blood will be taken. These samples will be stored in a designated central repository for the POPPY study. The analyses will be instigated only by the steering

committee of this trial and will not be for general Biobank access. Specific permission will be sought from all participants for this storage and also for any DNA analysis.

6.3 Neurocognitive testing

At baseline, study subjects are asked questions about their level of education and about their current occupational attainment. The National adult reading test will be undertaken providing an estimate of pre-morbid cognitive ability, (see study questionnaire in appendix 1).

During all study visits the following are assessed:

1. A short patient questionnaire, (see study questionnaire in appendix 1)
2. Staff administered neurocognitive testing
3. Computerised cognitive testing

These assessments are detailed below:

Patient questionnaire:

- A short questionnaire assesses patient's own perception of cognitive abilities.
- Difficulties in coping with complex activities of daily living are investigated with Lawton's questionnaire of Instrumental Activities of Daily Living.

Computerised cognitive testing

The computerised assessment will be performed on a desktop computer and will comprise of 8 tasks. This battery will require approximately 20 minutes to complete. The tasks are in the form of card games and specifically assess the following cognitive functions:

- simple and choice reaction time
- choice reaction time
- complex reaction time
- continuous performance
- one-back working memory
- matching
- incidental learning
- associate learning
- executive function
- verbal fluency and semantic memory

Subjects will be advised to consume no alcohol for at least 24 hours prior to this visit.

6.4 Respiratory Questionnaire

A respiratory questionnaire will be completed at visit 3 by the participant, with the aid of a member of the research study team, to assess patient's own perception of whether or not they have any breathing troubles and if so, whether it affects their daily life (see study questionnaire in appendix 1).

7.0 Study Management

Imperial College London will act as the nominated sponsor for this study. All project documentation will be submitted to the sponsor for approval prior to submission to regulatory bodies such as a Research Ethics Committee (REC).

The study will comply with the requirements of The Research Governance Framework (2nd Edition) and the ethical principles described in the current revision of the Declaration of Helsinki. The study will also be carried out in keeping with local legal and regulatory requirements.

Before the first subject is enrolled into the study all ethical and legal requirements must be met and ethics and R&D approval should have been obtained.

The REC and R&D offices and sponsor will be informed of all subsequent protocol amendments. Amendments will be evaluated to determine whether or not they are substantial and therefore if formal approval must be sought and whether the informed consent documents should also be revised.

The study will be coordinated from the Imperial Clinical Trials Unit (ICTU), which holds provisional registration as a UKCRC Trials Unit. An experienced study co-ordinator, based in the ICTU and working under the supervision of [name], will manage the day-to-day running of the study. Statistical support will be provided by a statistician working at UCL under the supervision of [name].

This study will not open to recruitment until appropriate approvals and authorisations have been obtained from an independent ethical committee. Recruitment will not commence at an individual participating site until local NHS Management approval has been obtained and all local documentation is in place and all requirements have been fulfilled according to ICTU Standard Operating Procedures (SOPs).

7.1 Adverse Events

Adverse event reporting for this study will be as follows:

All Adverse Events (AE) that are related to any of the study procedures outlined in the protocol (eg during blood testing, during DXA scanning) will be reported to the sponsor

All Serious Adverse Events (SAE) will be reported to the sponsor (both those related to study procedures and those which may not be related to study procedures)

All study-related adverse events, however minor, will be documented. An adverse event is any untoward medical occurrence in a subject administered a pharmaceutical product or, in the case of this study, in a subject undergoing a study procedure (including events that do not necessarily have a causal relationship with the study procedure). Adverse events observed by the Investigator, or reported by the subject, and any remedial action taken, will be recorded in the subject's CRF and should be verifiable in the subject's notes throughout the study. The nature of each event, time of onset (if known), after undergoing a study procedure will be documented together with the Investigator's opinion of the causal relationship to the study procedure (unrelated, unlikely, possible, probable, definite and not assessable). All subjects experiencing adverse events, whether considered associated with study procedures or not, must be monitored until the symptoms subside.

Severity should be recorded and graded according to the AIDS Clinical Trial Group (ACTG) Grading Scale.

Moreover, adverse events should be assessed in relation to their intensity, defined as follows:

MILD: the adverse event does not interfere with subject's usual function

MODERATE: the adverse event interferes to some extent with subject's usual function

SEVERE: the adverse event interferes significantly with subject's usual function

7.1.2 Serious Adverse Events (SAE)

A SAE is any untoward medical occurrence or effect that:

- **Results in death**
- **Is life-threatening – refers to an event in which the subject was at risk of death at the time of the event; it does not refer to an event which hypothetically might have caused death if it were more severe**
- **Requires hospitalisation, or prolongation of existing inpatients' hospitalisation**
- **Results in persistent or significant disability or incapacity – there is a substantial disruption of a person's ability to carry out normal life functions**
- **Is a congenital abnormality or birth defect**

An SAE form should be completed and faxed to ICTU for all SAEs within 24 hours of notification about the event. The ICTU will inform the following individuals within 24 hours of receiving notice of them:

1. The Sponsor (JRO, Imperial College London)

Sponsor:Imperial College London Sponsor No:CRO1992	Version 18.0	Page 18 of 44
---	--------------	---------------

2. Funders where contractually agreed
3. The Chief Investigators ([name] and [name])

Given the observational and non-interventional nature of this study, no additional information on SAEs will be captured.

At the study baseline visit, any SAEs occurring during the one year period leading up to entering the study will be assessed. Thereafter, at each yearly visit, SAEs occurring over the past year will be recorded.

All SAEs and AEs will be recorded on the annual study reports that are sent to the MHRA and REC.

Also, given the observational and non-interventional nature of this study, no serious, unexpected adverse drug reactions (SUSARs) reporting will be undertaken. As all subjects continue with their general clinical care, which is unaltered during the course of this study, the 'yellow card' reporting will be unaffected.

7.2 Monitoring

The Quality Assurance (QA) Manager will conduct a risk assessment with the assistance of the CI and Project Manager to assess the requirements for monitoring. A Monitoring Plan will be written accordingly. Monitors will be employed, trained and supervised by ICTU according to their SOP's. Monitoring will be implemented accordingly under the supervision of the Study Manager. Oversight of the trial will be conducted on a day-to-day basis by the QA Manager and the Director of Operations.

7.3 Quality assurance

The plans for the Governance of this study include the involvement of the ICTU QA Manager. The QA Manager will oversee the creation of all essential documentation to be used in this trial, which will be written with reference to the ICTU SOPs to ensure they comply with all ethical and regulatory requirements and are fit for purpose. The QA manager will also conduct a Risk Assessment on the study to ensure the development of an appropriate monitoring plan, which takes into account the particular requirements of this study.

7.4 Data management

Data will be collected via the Inform system. Inform is an Electronic Data Capture (EDC) tool that is used to collect subject information in an electronic case report form (eCRF). The system has a full audit trail built in via a secure internet interface as well as query and alert functionality, electronic signing of case books can be used at multiple sites and has multiple roles and functionality as well as workflow and reporting elements.

8.0 Statistical Considerations

8.1 Methods and planned analysis clinical manifestations

Detailed information on clinical events will be collected at baseline and at each visit. As we currently have very little data on the incidence, presenting features or outcomes of these events in older HIV-positive individuals, many of the analyses will be descriptive. We will describe the proportion of individuals in the three cohorts who have already experienced each event at baseline (prevalence) and the proportions who develop a new (or recurrent) event over follow-up (incidence). Confidence intervals will be generated for these proportions. Statistical comparisons of the prevalence/incidence of each event (where numbers are sufficiently large) will be performed using logistic/Poisson regression.

Sample size and power

The sample sizes for baseline analyses will be 1000, 500 and 500 respectively.

Based on data from Goulet *et al*⁵, we expect baseline prevalence rates of liver/renal disease of around 14.0%/4.6% among those aged >50 years versus 5%/1% in younger HIV-positive patients and 3.1%/2.3% in HIV-negative patients. Our study will have 70-100% power to detect similarly-sized differences between the three cohorts. Serious medical conditions are, however, expected to be rare, even in the older groups. For example, based on the limited data that exist (from various sources), we may see at most only 17, 20, and 7 cases of myocardial infarction, malignancy and liver failure, respectively, in the HIV-positive groups combined; analyses of incidence of these events will therefore be descriptive. Incident fractures and chronic kidney disease may be more common (105 and 100, respectively), but these numbers will still limit multivariable analyses. NC function impairment and current pain are expected to be present in 40% (n=540) and 63% (n=850) of the HIV-positive subjects at baseline; we will therefore have >95% power (5% significance level) to detect differences of 10% between the proportions with each event in the older HIV-positive and other cohorts; these sample sizes will also permit multivariable analyses of predictive factors. Among the older women (130 or so in the white/black African groups combined), we estimate that 70 (54%) will have already experienced the menopause at baseline; our analyses will be limited to simple comparisons of biomarkers in the two groups.

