	
Phone visit 2 (1st year follow up visit) – HIV negative cohorts only
 
4. Visit 3 (2nd year follow up visit)
 
The study visits are expected to take 1-2 hours to complete and will include the following assessments (see main protocol for full description)
 
 • Baseline demographics. • Socio-economic status. • Anthropometrics. • Lifestyle factors. • Quality of life assessment. • Full clinical history: to include history of non-AIDS co-morbidities • Menstrual and reproductive history (women) • Family medical history. • Current and recent antiretroviral use (over past 12 months). • Duration of HIV infection and date of HIV-seroconversion if known • Adherence assessment. • Use of any other medications. • Neurocognitive function assessment. • Pain assessment. • DXA scan A full body where available for bone mineral density, otherwise simple a scan of spine and hips will be performed. • Falls risk, Fracture risk, Frailty assessment • Most recent routine laboratory tests will be recorded and will be assessed in the HIV-negative cohort • Blood (serum, plasma, and PBMC) and urine samples stored Blood (plasma) will be collected for pharmacokinetic analysis (including but not limited to antiretroviral drug exposure)
Sample Size	Our choice of sample size is largely pragmatic, reflecting the number of older patients receiving care and the proportion that are expected to participate. Detailed sample size calculations are difficult given the wide range of topics and methodological approaches proposed. However, power calculations for some exemplar projects are provided.

1.1	Table of contents.	
1.0	Synopsis.....	3
1.1	Table of contents.....	5
2.0	Schedule of Visits	6
3.0	Introduction	7
3.1	Background – The HIV epidemic in the UK and Ireland	7
3.2	Clinical manifestations of ageing in HIV.....	7
3.3	Justification for the study.....	9
3.4	Study team	9
3.5	Summary	9
3.6	References.....	9
4.0	Study Plan	11
4.1	Study population	11
4.2	Setting	12
4.2.1	Recruitment of HIV-positive cohorts.....	12
4.2.2	Recruitment of HIV-negative cohort	13
4.3	Study Objectives.....	13
5.0	Study visits	13
5.1	Screening.....	13
5.2	Visit 1 (Baseline visit).....	13
5.3	Visit 2 (1st year follow up visit)	14
5.4	Visit 3 (2nd year follow up visit)	15
5.5	Withdrawal of subjects from study.....	15
5.6	Study timelines.....	16
5.7	Sub-Study	16
5.8	End of trial definition	16
6.0	Study Specific Procedures.....	16
6.1	DEXA scanning.....	16
6.2	Blood sampling	16

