4.2.1 Recruitment of HIV-positive cohorts

A list of individuals eligible for the older HIV-positive cohort will be generated at each clinic by study co-ordinators in collaboration with the lead consultant at the clinic, thus ensuring no unnecessary transfer of patient identifiable data out of the clinic. Patients will be randomly sampled from the list, with black African heterosexual men and women, and white heterosexuals (men or women) being over-sampled so that the final cohort includes 100 participants in each of these three groups. Clinic lists of younger patients attending each clinic will be stratified by age, gender, ethnicity and sexual orientation; eligible patients will then be sampled from these lists at a rate determined by the demographic profile of the older patients at the clinic.

Recruitment targets at each clinic are shown below in table 2:

Table 2: Recruitment targets at each site

Centre	Patients seen in 2008/09		Recruitment targets			Total
	<50 years	>50 years	HIV positive years	HIV negative years	>50 years	
St. Mary's Hospital	1406	317	60	120	60	240
King's College Hospital	1264	207	40	80	40	160
Chelsea & Westminster Hospital	3146	902	190	380	190	760
Homerton Hospital	445	73	15	30	15	60
Mortimer Market Centre	2246	468	90	180	90	360
Brighton and Sussex Hospital	1159	386	80	160	80	320
Mater Misericordiae University Hospital Dublin	536	65	25	50*	25	100
Total	10202	2418	500	1000	500	2000

*these subjects are already recruited into the Dublin HIV cohort study, therefore high rates of recruitment are considered feasible.

The recruitment target for Royal Free Hospital, open for recruitment as of November 2015, is as follows: 25 patients > 50 years HIV-positive; 13 patients < 50 years HIV-positive; and 13 HIV-negative controls (total of 51).

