8.2 Methods and planned analysis for pharmacokinetic analyses

Plasma drug concentrations from the older HIV-positive cohort will be compared with suggested minimally effective concentrations of each drug and to data from a large sample of historical HIV-positive controls obtained from a large therapeutic drug monitoring database held by the University of Liverpool. As plasma drug concentrations have a skewed distribution, non-parametric methods (e.g. Mann-Whitney tests) will be used. Proportional hazards regression will be used to investigate the impact of drug concentrations on time to virological failure (defined as two consecutive viral loads >50 copies/ml whilst remaining on treatment) after controlling for other confounders and adherence. All co-medications and drug doses, regardless of the prescriber, will be documented and the potential for drug-drug interactions investigated. Drug interactions will be defined as clinically significant (severe – drugs should not be co administered / potential interaction where dose adjustment may be necessary) or minor, and associations determined with any side effects reported.

Sample size

Based on current treatment guidelines, we anticipate that around 90% of older HIV-positive participants (n=810) will be receiving cART, with 60% of these patients (n=486) receiving tenofovir. These sample sizes are in excess of those generally used for other published studies of antiretroviral pharmacokinetics, providing further scope for multivariable analyses

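### Section 8.1's 70% power floor for liver/renal prevalence matches a different test from the planned one: under logistic regression the renal contrast with HIV-negative people has about 60-64%, and the contrasts covered are not named

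*Combined protocol and SAP*

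**What the plan says.** Section 8.1 (Sample size and power) sets the base: "The sample sizes for baseline analyses will be 1000, 500 and 500 respectively", in the order older HIV-positive, younger HIV-positive, HIV-negative. It takes expected liver/renal prevalences from a cited study: "14.0%/4.6% among those aged >50 years versus 5%/1% in younger HIV-positive patients and 3.1%/2.3% in HIV-negative patients". It then claims: "Our study will have 70-100% power to detect similarly-sized differences between the three cohorts". That sentence names no test, level, sidedness or list of contrasts.

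Earlier in the section, comparisons of prevalence and incidence "will be performed using logistic/Poisson regression". A 5% level, and the contrast of older HIV-positive people with the other cohorts, are given later in the paragraph, but for neurocognitive impairment and pain.

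The Synopsis sets the context: "Our choice of sample size is largely pragmatic", with power given for some exemplar projects.

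**The concern.** Expected renal prevalence in the older HIV-positive cohort is twice that in the HIV-negative cohort (4.6% v 2.3%), but both are low and the HIV-negative cohort has 500 people, so about 11 or 12 expected cases (500 × 0.023 = 11.5). A 70% floor looks high for that.

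This is the only pair that compares HIV status with both cohorts aged 50 or over. A 70% floor tells the reader that the chance of missing the expected doubling is at most 30%. If the planned analysis gives less, a null renal result would be read as more reassuring than it is.

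The phrase about differences between the three cohorts also leaves open whether younger HIV-positive v HIV-negative is covered. The expected differences there are small, and both cohorts have 500 people.

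**Working it through.** **Inputs (section 8.1).** Sizes 1000/500/500. Renal prevalence 4.6%, 1%, 2.3%; liver prevalence 14.0%, 5%, 3.1% (older HIV-positive, younger HIV-positive, HIV-negative). Test: logistic regression, taken as the model for prevalence and fitted without covariates. Two-sided 5% is assumed (z = 1.960).

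**Step 1: reproducing the printed range.** The upper end reproduces: liver disease, older HIV-positive v either other cohort, has power above 99.9% by the closed-form two-proportion formulas. The lower end can come only from renal disease, older HIV-positive v HIV-negative, with d = 0.046 − 0.023 = 0.023.

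- Unpooled standard error: SE1 = √(0.046×0.954/1000 + 0.023×0.977/500) = 0.009425.
- Pooled proportion: (46 + 11.5)/1500 = 0.03833. Null standard error: SE0 = √(0.03833×0.96167×(1/1000 + 1/500)) = 0.010516.
- Unpooled formula: Φ(0.023/0.009425 − 1.960) = Φ(0.480) = **68.5%**.
- Pooled formula: Φ((0.023 − 1.960×0.010516)/0.009425) = Φ(0.253) = **60.0%**.
- Pooled, one-sided 5% (z = 1.645): Φ((0.023 − 1.645×0.010516)/0.009425) = Φ(0.605) = **72.7%**.

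So the printed 70% lies close to the unpooled two-sided result and to the pooled one-sided result. An overall three-group test of renal prevalence gives 95% (noncentral chi-square) to 98% (simulated likelihood ratio), so the 70% does not come from that reading.

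**Step 2: the planned analysis.** Each possible pair of case counts is weighted by its binomial probabilities, and the weights of the pairs in which the unadjusted logistic test rejects are added up.

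| Contrast | Outcome | Pooled formula | Logistic, Wald | Logistic, likelihood ratio |
|---|---|---|---|---|
| Older HIV-positive v HIV-negative | Renal | 60.0% | 60.1% | 64.3% |
| Older v younger HIV-positive | Renal | 98.1% | 97.9% | 99.0% |
| Older HIV-positive v HIV-negative | Liver | >99.9% | >99.9% | >99.9% |
| Older v younger HIV-positive | Liver | 99.99% | 99.99% | 99.99% |
| Younger HIV-positive v HIV-negative | Renal | 36.4% | 31.2% | 38.3% |
| Younger HIV-positive v HIV-negative | Liver | 33.1% | 31.7% | 33.5% |

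For the first row, the chance of missing the difference is 100 − 64.3 = 35.7% to 100 − 60.1 = 39.9%, against the 30% implied by the text.

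**Step 3: the base used elsewhere in section 8.** Section 8.1 puts neurocognitive impairment and pain as "expected to be present in 40% (n=540) and 63% (n=850) of the HIV-positive subjects at baseline": 540/0.40 = 1350 and 850/0.63 = 1349, against 1000 + 500 = 1500 (which would give 600 and 945). Section 8.2 says "we anticipate that around 90% of older HIV-positive participants (n=810) will be receiving cART": 810/0.90 = 900, against 1000 (which would give 900 people on cART). The documents do not explain the smaller base.

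**The case against.** The strongest reply is that 70% is a fair rounding. The unpooled two-proportion formula is standard for an exemplar calculation and gives 68.5%. The prevalences are stated as approximate: at the favourable edge of rounding (4.65% v 2.25%) the unpooled formula gives 72.4%, and at the unfavourable edge (4.55% v 2.35%) 64%. Adding the later Royal Free targets in section 4.2.1 ("25 patients > 50 years HIV-positive; 13 patients < 50 years HIV-positive; and 13 HIV-negative controls") gives 69.5% at 1025/513. This stands as a defence against a charge of miscalculation, which a reader might otherwise infer. It does not make 70% the power of the planned regression, which is 64-68% at the favourable edge, 56-60% at the unfavourable edge and 61-65% at 1025/513.

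Second, the word 'versus' in the prevalence sentence, and the contrast named for neurocognitive impairment and pain, suggest that only older HIV-positive v each other cohort was meant. That is the more natural reading. On it, the 31-38% for the third pair shows an ambiguity of wording, not a false figure, and only one contrast is in question.

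Third, the omissions belong to one sentence. The section does name the regression, and it gives a 5% level for the neighbouring calculation. Only sidedness appears nowhere in it.

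Fourth, a reader might take the implied base of 900 older HIV-positive people to mean that power is lower still (logistic 55-60% at 900/450). The documents do not support using that base here. Section 8.1 states 1000/500/500 just before this claim, the smaller counts belong to other calculations, and 450 HIV-negative people would be an assumption.

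**Conclusion.** The 70% floor is not delivered by the analysis that section 8.1 plans. For renal disease, older HIV-positive v HIV-negative, power is about 60-64%, which is 6 to 10 points lower. The other three older HIV-positive contrasts have about 98% or more. Younger HIV-positive v HIV-negative, covered only on a literal reading, has about 31-38%.

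This rests on the printed sizes and prevalences, a two-sided 5% level (assumed), no multiplicity adjustment and an unadjusted model; covariate adjustment was not modelled.

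Two stronger conclusions are tempting and do not follow. One is that the sponsor miscalculated: the printed figure is close to a recognised formula. The other is that the study is too small: the size is pragmatic, the calculation is an exemplar, and section 8.1 says that many analyses will be descriptive, with confidence intervals. What is affected is how this comparison is described and how a null renal result is interpreted.

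**What to change.** In section 8.1, replace the power sentence with:

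*With 1000, 500 and 500 participants, unadjusted logistic regression and a two-sided 5% level, power is about 98% or more for older v younger HIV-positive (liver and renal) and for older HIV-positive v HIV-negative (liver), and about 60-64% for older HIV-positive v HIV-negative (renal); younger HIV-positive v HIV-negative (about 31-38%) is outside this claim.*

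If the sponsor intended another level, sidedness or test, state it and give the matching figures.

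Separately, reconcile the counts of 540 and 850 (section 8.1) and 810 (section 8.2) with the stated 1500 HIV-positive and 1000 older HIV-positive participants, or say why a smaller base applies to those calculations.

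The cost is wording only. One stated figure becomes less favourable. Enrolment, visits and data collection do not change.

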4.3 Study Objectives

Clinical manifestations

- To describe the incidence and presenting features of serious medical conditions (such as cardiovascular, liver, renal disease, cancer and fragility fractures) in the three cohorts.
- To describe the outcomes of serious medical conditions (including time to recovery/resolution, where applicable, the incidence of complications and use of health-care).
- To compare NC function in the three cohorts, and to identify predictors of NC function.
- To compare the levels of musculoskeletal pain in the three cohorts, to identify predictors of this and to describe the health-care needs of those affected.
- Among women, to assess the effects of menopausal status on cardiovascular disease, BMD and lipid/glucose metabolism.

Antiretroviral pharmacokinetics and drug interactions

- To describe plasma (or, where appropriate, intracellular) concentrations of antiretroviral agents (tenofovir, non-nucleoside reverse transcriptase, protease, integrase and entry inhibitors) at baseline in the older HIV-positive cohort, and to compare these to those seen in younger HIV-positive patients.
- To describe the incidence of toxicities/drug discontinuations and immunological/virological responses to cART in the HIV-positive cohorts and to assess correlations between these events and plasma drug concentrations.
- To describe the level of poly-pharmacy in the older HIV-positive cohort and thus the potential for/prevalence of unwanted drug-drug interactions.
- To determine whether accumulation of renally-excreted antiretroviral drugs (e.g. tenofovir) increases their potential to cause renal injury in older HIV-positive people.

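### The only neurocognitive comparison that section 8.1 specifies is the proportion impaired; a continuous-score model that uses the reading test and education should be added

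*Combined protocol and SAP*

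**What the plan says.** The NC objective in section 4.3 is about function and its predictors: "To compare NC function in the three cohorts, and to identify predictors of NC function".

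Section 6.3 describes a computerised battery that includes simple, choice and complex reaction time, working memory and learning. Education is asked about at baseline, and a reading test is given: "The National adult reading test will be undertaken providing an estimate of pre-morbid cognitive ability". The visit schedule in section 2.0 places NC assessment at Visits 1 and 3.

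Section 8.1 treats clinical outcomes as events. They are summarised as proportions, and the method given is: "Statistical comparisons of the prevalence/incidence of each event (where numbers are sufficiently large) will be performed using logistic/Poisson regression". NC function enters only as an impairment proportion: "NC function impairment and current pain are expected to be present in 40% (n=540) and 63% (n=850) of the HIV-positive subjects at baseline". The power claim that follows is "we will therefore have >95% power (5% significance level) to detect differences of 10% between the proportions" for older HIV-positive participants against the other cohorts. The same sentence adds that "these sample sizes will also permit multivariable analyses of predictive factors". No summary score, definition of impairment, continuous-score model or covariate list is given for NC function.

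**The concern.** The objective is about level of function, but the only comparison set out is of a dichotomy. Cutting a graded score into impaired or not treats everyone on one side of the cut as alike. That costs precision, and it leaves only movement across the cut as a measure of change between visits.

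Prior ability is a separate matter. Section 4.2.1 samples younger patients by age, gender, ethnicity and sexual orientation, and education is not in that list. Section 4.2.2 recruits HIV-negative volunteers from clinics, press, community organisations, internet sites and churches. The cohorts may therefore differ in education or pre-morbid ability, and such a difference can pass for an effect of HIV or age. The study collects the variables that would address this but does not say how they will be used. The summary score, cut-off and covariates could then be chosen after the data are seen.

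**Working it through.** **Inputs from section 8.1.** Impairment 40%; difference 10 points; 5% level (two-sided assumed); cohorts of 1000, 500 and 500. **Assumed, because the documents are silent:** one normally distributed NC score, equal SDs, and cohorts that differ by a shift in mean.

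**1. The plan's own figure.** Power = Φ[(Δ − 1.96·SE0)/SE1], where SE0 uses the pooled proportion and SE1 the separate ones.

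For 40% of 1000 v 50% of 500:
- pooled p = 650/1500 = 0.4333
- SE0 = √(0.4333 × 0.5667 × 0.003) = 0.02714
- SE1 = √(0.24/1000 + 0.25/500) = 0.02720
- power = Φ[(0.1 − 0.0532)/0.0272] = Φ(1.72) = 95.7%

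For 40% v 30% the same formula gives 97.0%. The claim of more than 95% reproduces.

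The count of 540 at 40% implies 540/0.40 = 1350 HIV-positive participants, not the 1500 that the stated cohort sizes give. At 900 v 450 the two powers are 93.7% (40% v 50%) and 95.3% (40% v 30%). The range is therefore about 94% to 97%.

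**2. Information lost by the cut.** Relative efficiency of the dichotomy = φ(z_p)²/[p(1 − p)].

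| Share impaired | φ(z_p) | Efficiency | Loss |
|---|---|---|---|
| 30% | 0.3477 | 0.576 | 42.4% |
| 40% | 0.3863 | 0.622 | 37.8% |
| 50% | 0.3989 | 0.637 | 36.3% |

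At 40%: 0.3863²/0.24 = 0.622.

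**3. What this means for power at 1000 v 500.** The SE of a mean difference in SD units is √(1/1000 + 1/500) = 0.0548. Each pair of proportions is converted to a shift d = z(p2) − z(p1), and continuous power = Φ(d/0.0548 − 1.96).

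| Contrast | Shift | Binary power | Continuous power |
|---|---|---|---|
| 40% v 50% | 0.253 SD | 95.7% | 99.6% |
| 40% v 45% | 0.128 SD | 45.7% | 64.5% |

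The 5-point row is an illustration and is not a target in the plan. The shift detectable with 95% power falls from about 0.25 SD (binary) to (1.96 + 1.645) × 0.0548 = 0.20 SD (continuous).

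**4. Prior ability (illustration, all inputs assumed).** If two cohorts differ by 0.2 SD in prior ability, and its correlation with the NC score is 0.3 to 0.7, the spurious shift is 0.2 × 0.3 = 0.06 to 0.2 × 0.7 = 0.14 SD. From a 40% base this looks like Φ(−0.253 + 0.06) = 42% to Φ(−0.253 + 0.14) = 45% impaired with no true effect. Adjustment would also multiply the residual variance by 1 − ρ², that is 0.91 to 0.51.

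**5. Why age must not be a blanket covariate.** Section 4.1 defines the two HIV-positive cohorts by age under 50 and 50 or over, so their ages do not overlap. With a 2:1 split, the variance inflation for the cohort contrast is 1 + (2/9)D²/s², where D is the mean age gap and s² the within-cohort age variance. The ages below are assumed.
- Younger mean 37 (SD 9), older mean 56 (SD 8): s² = (2 × 64 + 81)/3 = 69.7; inflation 1 + 80.2/69.7 = 2.2.
- Younger mean 35 (SD 8), older mean 60 (SD 5): s² = (2 × 25 + 64)/3 = 38; inflation 1 + 138.9/38 = 4.7.

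Before any gain from lower residual variance, efficiency would be roughly 21% to 46%. That is worse than the 62% of the dichotomy.

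**The case against.** The strongest reply is that the 40% figure sits in a power paragraph, and the synopsis describes the power calculations as exemplars. The objective is not restricted to a binary outcome. Multivariable analyses are foreseen, and section 8.3 plans associations with patient factors. All of this stands. A reader might infer that a continuous analysis is ruled out, or that the cohorts will be compared unadjusted. The documents support neither: they leave the score unmentioned and the covariates unnamed, and an impairment definition might already draw on the reading test.

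A reader might also infer that change over 24 months is not measured at all. Section 8.1 plans the proportion with a new event over follow-up. If impairment counts as an event, that is a measure of change, though a coarse one.

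Finally, the 38% depends on a distribution that the documents do not give, and the plan's 10-point comparison is already well powered. Both points are right, and they limit the size of the concern. They do not remove it, because the one NC comparison that is stated is less efficient than an alternative that needs no new data collection.

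**Conclusion.** The point holds as a worthwhile improvement and does not threaten the study. The only NC comparison specified is a proportion impaired, and the reading test and education have no stated role in the analysis. Under normality and equal SDs the cut at 40% loses about 38% of the information (36% to 42% for cuts of 50% to 30%). A skewed or multi-part score would give a different figure.

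It would be wrong to conclude that the study is underpowered for NC impairment. Its own 10-point baseline difference has about 94% to 97% power. The benefit lies in smaller differences, predictors and change from Visit 1 to Visit 3, and in less confounding by prior ability in cohorts with no stated matching on education.

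**What to change.** In section 8.1:

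- Define the NC summary score and the definition of impairment before analysis.
- Add a linear model of a composite z-score, standardised on the HIV-negative cohort with skewed tasks transformed first, adjusted for education and reading-test score. Report it alongside the proportion impaired.
- Adjust for age in the older HIV-positive v HIV-negative comparison only. In the older v younger HIV-positive comparison, age adjustment would remove the contrast that defines the cohorts and inflate its variance.
- For Visit 1 to Visit 3, compare within-person change, or fit a repeated-measures model with a cohort-by-visit term. Conditioning on the Visit 1 score can bias the comparison, because the cohorts are not randomised, may differ at baseline, and are measured with error.
- Reconcile the counts of 540 and 850, which fit 1350 HIV-positive participants, with the stated cohort sizes.

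The cost is plan wording and modest extra analysis, since the variables are already collected. A z-score is less directly clinical than a proportion, which is why the proportion impaired should still be reported.
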